Our study will focus on female concussions because concussions tend to be more prevalent in females, and regardless of study sample or injury mechanism (sports[12], civilian, military), women (compared to men), report greater concussion morbidity (prolonged recovery, worse physical, cognitive and psychosocial symptom reporting[13, 14], [40]), and experience poorer treatment pathways[14]. **Interestingly, women also report greater PTG after trauma, but no research has evaluated the intersection of PTG and mTBI in female concussion survivors. Not only will we be filling this gap in the field, but we will take the work further and conduct a pilot assessment of whether mindfulness based interventions such as yoga, which have been shown to improve mTBI sequelae[2], also improve PTG for individuals with low PTG in the study sample. This pilot intervention is not only important for exploring protective recovery pathways, but also aligns with emerging research advocating for exercise as medicine for concussion [2, 15, 16].**

Thus, the aims of this research are to:

Aim 1: a) Determine the prevalence of low PTG in a population of female concussion survivors.

*We hypothesize that at least 35% of the study sample will have low PTG (score <75 on PTG scale)[17]*

Aim 1b) Determine what (concussion-related factors) predict low PTG.[18]

*We hypothesize that predictors of low PTG will include: older current age[19], older age at time of injury[19], non-White race[20], history of multiple concussions, high burden of post-concussion symptoms, and high burden of mood disorders (Anxiety, depression) and PTSD*

[figure not shown]
Aim 1c) Identify which of the 5 PTG domains are least prevalent and could be targeted for future interventions.

Aim 2: a) Determine if a pilot yoga intervention improves PTG scores for individuals with low PTG.

*We hypothesize that PTG scores will increase after the yoga intervention for those with low PTG who partake in the intervention.*

Aim 2b) Identify which of the 5 PTG domains (in Aim 1c) are improved by the intervention

Figure 5: Schematic Diagram of the Project

[figure not shown]

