We are requesting a waiver of documentation of consent as participants will be recruited online using an IRB approved consent form that will be on the study's landing page. Upon clicking the survey invitation link, potential survey takers will be brought to the very first page of the survey which will be the IRB-approved consent page. This will list the risks, benefits, incentives, and overall research processes. The consent will also state that the research is no greater than minimal risk and involves procedures for which written consent is normally not required outside of the research context. After reviewing the approved information sheet, participants will be prompted to consent yes in order to move on to the survey body. Those who do not consent will be sent to a "Thank you page" and not continue. Those who do so, will begin the survey. All survey questions will be voluntary and responses will be de-identified and analyzed in aggregate to ensure anonymity.

We are also requesting a waiver of Vincent cards for incentives, as we will be using e-gift cards for providing incentives to the study participants. We will collect PHI (full name, email, address, etc.) to incentivize participants. Collected PHI will be removed in the final data set, after all incentives are provided to those who complete the study, including the Yoga intervention (if they are selected). PHI will not be reused or disclosed to any other person or entity outside of the scope of this research except (i) as required by law, (ii) for authorized oversight of the research study, or (iii) for other research for which the use or disclosure of PHI would be permitted by the HIPAA Privacy Rule.

- a) **Number of Subjects:** We seek to have at least 350 participants using an alpha of 0.05, 95% confidence interval and a low PTG prevalence of 35%.
- b) **Gender and Age of Subjects:** To be eligible for this study, participants must be at least 18 years of age. There is no gender or gender identity restriction.
- c) **Racial and Ethnic Origin:** Enrollment will not be based upon racial or ethnic origin.

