#### Demographics and other injury-related attributes

We will design a survey to collect basic demographic and injury-related variables such as current age, age at time of injury, parity, marital status, history of previous concussions, number of previous concussions, educational attainment, services they are currently receiving, etc.

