#### DATA ANALYSIS PLAN

We will initially use univariate analyses and descriptive statistics to examine the frequencies and distributions of the data. Established cut-offs will be used to define the low and high PTG groups, and compare the

distribution of PTG domains, PCS, mood and PTSD between the groups. In bivariate analyses, we will use Chi-square tests ( $\chi^2$ ) to compare differences between the low PTG and high groups across various demographic and injury-related factors. Variables that meet a p-value cutoff of  $p < 0.2$  during the bivariate analyses will be included in adjusted regression models. We are using a  $p < 0.2$  cutoff instead of  $p < 0.05$  to be conservative, since this is the first exploration of PTG outcomes in a female concussion sample that we are aware of. Crude and adjusted logistic regression models will be used for effect estimates and prediction models, using a significance level of  $p < .05$

For Aim 2, we will use paired t-test to compare the mean difference in PTG scores and domains before and after the yoga intervention to determine its effectiveness. We will administer the PTG surveys again at 7 weeks and 30 days to 15 Yoga and 15 Wait list controls (see Figure 5). The 15 Yoga participants will also do the post-yoga assessments at 7 weeks. The 15 Wait list controls will do the LYB program after the 30-day PTG surveys have been completed. The 15 Wait list controls will receive a follow up survey, 1 week after the completion of the LYB program. The intervention group participants who have attended 3 or more LYB yoga sessions will also receive a week-20 follow up survey and the participants who complete the survey will receive \$30 incentive.

To evaluate the feasibility & acceptability of the intervention, we will collect the following metrics:

- A) Overall Yoga intervention **interest rate**=# interested in participating in Yoga/total # participants (how many PINK women are interested in the Yoga overall? If high can speak to using Yoga as an effective intervention for this population. If low, explore reasons)
- B) PTG-specific interest rate: #interested participants with low PTG (score <75)/total #participants (how many people with low PTG are interested in Yoga? We expect this proportion to be lower than overall metric in A above)
- C) Yoga intervention participation rate=# who enroll in LYB program (n=30)/#interested participants with low PTG (We will invite 30 people to participate so we know the numerator)

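### Aim 1b names eight predictors of low PTG in advance, but the only stated way into the adjusted model is an unadjusted bivariate p<0.2, so a hypothesised predictor can end with a crude odds ratio only

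*Combined protocol and SAP*

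**What the plan says.** Aim 1b, in the list of aims that closes the background, is to "Determine what (concussion-related factors) predict low PTG". Its hypothesis is specific and has directions: "predictors of low PTG will include: older current age[19], older age at time of injury[19], non-White race[20], history of multiple concussions", followed by "high burden of post-concussion symptoms, and high burden of mood disorders (Anxiety, depression) and PTSD". Counting anxiety, depression and PTSD separately, that is eight predictors.

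The Data Analysis Plan first compares symptoms, mood and PTSD between the low and high PTG groups. It then describes chi-square tests, and that sentence mentions only demographic and injury factors. Next comes the entry rule: "Variables that meet a p-value cutoff of" 0.2 "during the bivariate analyses will be included in adjusted regression models". The reason given for 0.2 rather than 0.05 is that this is a first exploration in this population. The modelling sentence is: "Crude and adjusted logistic regression models will be used for effect estimates and prediction models". No section lists the covariates of the adjusted model or exempts the Aim 1b predictors from the rule.

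The section on demographics and injury attributes lists "injury-related variables such as current age, age at time of injury, parity, marital status, history of previous concussions" and further items as examples. Race is not among them.

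**The concern.** A hypothesis stated in advance should be answered whatever the data show. Here the sample's unadjusted p-values decide which of the eight hypotheses receive an adjusted OR and confidence interval. One that misses the cutoff is answered only by a crude OR, which carries whatever confounding exists. The adjusted ORs of the retained predictors also lose that variable from their adjustment set, so what they are adjusted for depends on the sample.

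The standing of four of the eight is also unclear. If the p<0.2 rule covers only the variables in the chi-square sentence, the post-concussion, anxiety, depression and PTSD scales have no stated way into the adjusted model.

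**Working it through.** **The plan's own figure.** The section on power gives n=350 for 35% prevalence and a 95% confidence interval. The precision formula reproduces it if a half-width of 5 points is assumed: 1.96² × 0.35 × 0.65 / 0.05² = 349.6, so 350. The stated 80% power cannot be reproduced, because no effect size is given for any Aim 1b predictor. Every OR, exposure share and correlation below is therefore an assumption.

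**Step 1: one binary predictor.** Let q be the share exposed. The risks p0 and p1 are chosen so that their odds ratio is the assumed OR and q·p1 + (1−q)·p0 = 0.35. With d = p1 − p0, the chance of passing a two-sided 0.2 screen is Φ[(d − 1.2816·se0)/se1] plus a negligible opposite tail. Here se0 is the pooled standard error of the difference and se1 the unpooled one.

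Example, OR 1.5 and q = 0.5 (175 per group): p0 = 0.304, p1 = 0.396, d ≈ 0.092, se0 = √(0.35 × 0.65 × 2/175) = 0.051, se1 ≈ 0.051. The argument is about 0.52, so the predictor passes in about 70% of studies and misses in about 30%.

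| Share exposed | 50% | 30% | 20% | 10% |
|---|---|---|---|---|
| Misses p<0.2, OR 1.5 | 30% | 34% | 42% | 55% |
| Misses p<0.2, OR 2.0 | 4% | 6% | 10% | 26% |

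**Step 2: all eight together, by simulation.** Assumptions: all effects in the hypothesised direction, 20% non-White, 50% with multiple concussions, the two ages correlated 0.8, the four scales correlated 0.5, groups otherwise independent, and a crude logistic test at 0.2 as the screen.

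| Scenario | At least one of eight lost | Lost although p<.05 in the eight-predictor model |
|---|---|---|
| A: binary ORs 1.5, others 1.2 per SD | 72% | 1.0% |
| B: binary ORs 1.5, others 1.1 per SD | 91% | 3.2% |
| C: binary ORs 2.0, others 1.2 per SD | 36% | 1.0% |

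In scenario A the losses are concentrated in race (49%) and multiple concussions (35%). Each age is lost in about 8% and each scale in under 1%.

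**Step 3: sensitivity.** The simulated screen treats ages and scales as continuous, whereas the plan names chi-square tests and gives no categories. If they are split at the median and tested by chi-square, scenario A rises to about 80%. If 40% rather than 20% are non-White, A falls to about 67% and C to about 30%. So the figures show order of magnitude and do not forecast this study.

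**Step 4: can the sample carry all eight?** 0.35 × 350 = 122.5 low-PTG women. At one parameter per predictor, 122.5 / 8 = 15.3 per parameter. Questions can be skipped ("All survey questions will be voluntary and responses will be de-identified"). If 20% of records were incomplete (assumed), 0.8 × 122.5 = 98, and 98 / 8 = 12.3. Sample size does not force the hypothesised predictors to be screened.

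**The case against.** **The rule only includes; it does not expressly exclude.** On a generous reading, the screen picks adjustment covariates, and each factor of interest gets both a crude and an adjusted estimate. It is true that exclusion is not spelled out. But the text does not limit the rule to covariates, and a cutoff that did not govern entry would have no purpose. Equally, a reader might infer that all eight are certainly screened. The chi-square sentence does not support that for the four scales.

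**The cutoff is deliberately lenient, for a first exploration.** That is a fair reason for screening variables without a hypothesis, such as parity. It is weaker for predictors already named with a direction. Leniency reduces the loss but does not remove it.

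**Little inference is lost.** This stands. A reader might infer that the screen would often hide significant predictors, but scenarios A to C put that at about 1% to 3% of studies. Frequent masking needs effects that oppose each other. With adjusted ORs of 1.5 and 0.67 per SD correlated at 0.3, 0.5 and 0.7, the first predictor is dropped although significant in 5%, 19% and 32% of studies. Aim 1b hypothesises no such opposition. With both ORs 1.5 and positive correlation the figure is essentially zero. With both ages at OR 1.2 per SD, correlated 0.8 or 0.9, it is 0.2% or 0.4%.

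**Readers would be misled.** A reader might infer that an absent adjusted association could not be told from one never estimated. That does not follow: crude models are planned, and a crude OR with no adjusted OR beside it shows what happened.

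**Conclusion.** The point holds as a gap in model specification that is cheap to close. The documents fix the hypotheses in advance but let an unadjusted p-value decide which of them get an adjusted estimate, and they leave the entry of the four scales unclear. Under the assumed inputs, losing at least one of the eight is common (roughly 36% to 91% across scenarios A to C), with race and multiple concussions most exposed when their ORs are near 1.5. The consequence is moderate: missing adjusted ORs and intervals, and incomplete adjustment of the others, with rare loss of a significant result. The reading of the rule comes from the text; the percentages depend on the assumed ORs, shares, correlations and form of screen.

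**What to change.** Prespecify one primary adjusted logistic model for low PTG that contains all the Aim 1b predictors whatever their bivariate p-value, with ages and scale scores continuous. Report every adjusted OR with its 95% confidence interval. Keep p<0.2 screening for other covariates, such as parity, marital status and education, in a separate model labelled exploratory.

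For the two ages, state that when both are in the model the OR for age at injury, at fixed current age, reflects time since injury. Also report each age's OR from a model without the other, so that each age hypothesis is answered.

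Confirm that the survey asks race. The other variables are already collected, so the rest is SAP wording.

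The cost is precision. For four equally correlated scales the standard error rises by √VIF, where VIF = (1 + 2r)/[(1 − r)(1 + 3r)]: about 10%, 26% and 61% at r = 0.3, 0.5 and 0.7. For the two ages the factor is 1/√(1 − r²): about 67% and 129% wider at r = 0.8 and 0.9. The correlations are assumed.

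### Aim 1b screens variables against low PTG at p<0.2, then reports ordinary p-values, intervals and a prediction model from the same women, with no allowance for the selection and no internal validation

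*Combined protocol and SAP*

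**What the plan says.** All from the combined protocol and SAP.

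- **Aim.** Aim 1b, in the list of aims that closes the Background, is to "Determine what (concussion-related factors) predict low PTG". Its hypothesis names eight factors: current age, age at injury, race, multiple concussions, post-concussion symptom burden, anxiety, depression and PTSD.
- **Outcome.** In the Data Analysis Plan, "Established cut-offs will be used to define the low and high PTG groups"; low means a PTGI-X score below 75.
- **Screen.** Chi-square tests are used "to compare differences between the low PTG and high groups across various demographic and injury-related factors". Variables with p<0.2 "during the bivariate analyses will be included in adjusted regression models". The looser cut-off is described as conservative, "since this is the first exploration of PTG outcomes in a female concussion sample that we are aware of".
- **Inference.** Next, "adjusted logistic regression models will be used for effect estimates and prediction models, using a significance level of" p<.05.
- **Candidates.** Under Demographics and other injury-related attributes, the list of survey variables ends with "educational attainment, services they are currently receiving, etc", so it is not closed.

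The eight hypothesised factors are neither forced into the model nor exempted from the screen. No split sample, cross-validation, bootstrap, shrinkage, multiplicity adjustment or performance measure is described. The Limitations section raises Type 2 error for the yoga pilot and says nothing about selection or overfitting.

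**The concern.** An ordinary logistic p-value or interval is valid for a model chosen without looking at the outcome. Here a variable is in the adjusted model because it already showed some association with low PTG in the same data. Its p-value and interval are then read as if it had been there from the start. The same model is also meant for prediction, and nothing corrects for choosing and fitting it on one sample.

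What Aim 1b delivers is a list of factors said to predict low PTG. A reader of the final table sees only the variables that survived, so the error rate among survivors is the one that matters to that reader.

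**Working it through.** **1. The plan's own figure.** The sample size is 350, for 35% low PTG. The usual precision formula is n = 1.96² × 0.35 × 0.65 / d². With a half-width d of 0.05 (not stated; assumed), n = 3.8416 × 0.2275 / 0.0025 = 349.6, which rounds up to 350. Half-widths of 0.04 and 0.06 give 547 and 243. So 350 matches a prevalence estimate good to ±5 points. The stated 80% power cannot be reproduced, because no alternative is given. Expected low-PTG events: 350 × 0.35 = 122.5.

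**2. Analytic check, no true predictors.** A noise variable enters with probability 0.20. It would reach p<.05 with probability about 0.05, and nearly always passes the screen when it does. Given entry, the rate is therefore about 0.05 / 0.20 = 25%, and a nominal 95% interval covers no effect about 75% of the time. Per candidate tested, the rate is 0.20 × 0.25 = 5%.

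**3. Simulation, no true predictors.** Inputs from the plan: N = 350, 35% low PTG, chi-square screen at p<0.2, then multivariable logistic regression at p<.05 (two-sided assumed). Assumptions: binary candidates, their number, and a correlation of 0 or 0.3 on the underlying scale. There were 2,000 runs per row. The comparator is one model with all candidates and no screen.

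| Candidates, correlation | Significant given entry | Significant per candidate | Any false predictor: screened / unscreened | Mean apparent AUC: screened / unscreened |
|---|---|---|---|---|
| 8, 0 | 23.3% | 4.8% | 32.7% / 33.9% | 0.571 / 0.588 |
| 8, 0.3 | 21.5% | 4.3% | 27.6% / 33.5% | 0.568 / 0.587 |
| 15, 0 | 24.6% | 5.0% | 51.8% / 56.7% | 0.594 / 0.623 |
| 15, 0.3 | 21.3% | 4.2% | 42.2% / 55.3% | 0.587 / 0.621 |
| 25, 0 | 25.5% | 5.2% | 71.9% / 76.9% | 0.624 / 0.660 |
| 25, 0.3 | 20.5% | 4.1% | 60.8% / 75.2% | 0.610 / 0.658 |

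Thirteen candidates is the count actually named: the eight hypothesised, plus parity, marital status, number of concussions, education and services. Repeated runs with 13 binary candidates gave any false predictor in 46-50% (independent) and 38-39% (correlated) of datasets, against 48-51% and 49% unscreened. Apparent AUC was about 0.58-0.59 screened and 0.61 unscreened. Plain multiplicity predicts 1 − 0.95^8 = 33.7% and 1 − 0.95^13 = 48.7%.

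AUC on fresh outcomes is 0.50 in every row. The screened AUC averages over datasets in which something entered. With 8 independent candidates nothing entered in 16.0% of datasets; scoring those at 0.50 gives 0.160 × 0.50 + 0.840 × 0.571 = 0.56.

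**4. With true predictors present.** With four true predictors among 12 or 20 candidates, uncorrelated with the noise, 26% of entered noise variables were significant. With correlation 0.3, about 72% of noise variables entered and only 2.6-2.8% of those were significant. Other assumed settings (two or four true predictors, odds ratios 1.5-2.0, correlation 0.3-0.5) gave 2.7-7.3%.

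**5. Does repeating the screen in a bootstrap help?** In 100 null datasets with 40 resamples each, mean AUC fell from 0.56 to 0.50 with 8 candidates and from 0.61 to 0.52 with 20.

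**The case against.** The strongest reply is that 20-25% is a change of denominator. It is 0.05 divided by 0.20; per candidate tested, the rate stays at 4-5%. A reader might infer that the screen makes each noise factor four or five times as likely to be declared a predictor, or that it causes the sizeable chance of at least one false predictor. Neither follows: an unscreened model with all candidates has about the same chance or a higher one. This part of the reply stands.

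The 20-25% also does not hold generally. Several hypothesised factors are plainly related to one another (the two ages; anxiety, depression, PTSD and symptom burden). If some are true predictors, correlated noise mostly enters and then loses significance on adjustment. This stands too.

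A reader might further infer that the model will look strongly predictive. An apparent AUC of 0.57-0.59 is weak, an unscreened model shows slightly more optimism, and the plan promises no AUC and no whole-model test. The fault there is missing validation more than the screen.

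Finally, the plan calls this a first exploration, the crude models are not affected by the selection if reported for every candidate, and a loose cut-off is defensible for retaining confounders. Eligibility for yoga does not depend on Aim 1b. These points limit the harm. They do not make the reported p-values and intervals valid, because the plan still applies p<.05 to the selected model and intends it for prediction.

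**Conclusion.** The point holds in limited form. P-values and 95% intervals for variables that pass the screen are not valid at their nominal level. If nothing predicts, or noise is uncorrelated with true predictors, about 20-25% of surviving noise variables reach p<.05, and this hardly depends on the number of candidates. With noise correlated with true predictors the rate can be about 3%, so the nominal 5% can be wrong in either direction.

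The chance of any false predictor, about 28-34% with 8 candidates and 38-50% with 13 binary ones, is ordinary multiplicity and should not be charged to the screen. Any AUC reported without validation would average about 0.57-0.59 when the truth is 0.50; the unscreened figure is 0.59-0.61.

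These figures rest on N = 350, 35% low PTG, binary candidates and assumed candidate counts and correlations. The change is worth making because it affects what Aim 1b can claim; it does not touch Aim 2.

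**What to change.** In the Data Analysis Plan:

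1. For Aim 1b, replace the p<0.2 screen by one pre-specified adjusted logistic model containing all eight hypothesised predictors, and report all eight estimates whatever their p-values. With about 122 events this is 122.5 / 8 = about 15 events per coefficient if each factor takes one coefficient.
2. Label any other variables brought in by screening as exploratory.
3. For any prediction model, bootstrap the whole model-building procedure, repeating the p<0.2 screen in each resample if it is kept. Report optimism-corrected AUC and calibration slope.

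The fixed model makes each p-value mean what it says: in the unscreened simulations 5.0-5.9% of noise coefficients reached p<.05. It does not remove multiplicity across the eight tests.

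The cost is a few sentences and some extra programming, with no new data or participants. Intervals will be somewhat wider because all eight variables are included, and the reported AUC will be lower.

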#### The LYB Yoga intervention

Thirty participants will be randomly selected to participate in the LYB Yoga intervention ([An overview of randomization techniques: An unbiased assessment of outcome in clinical research - PMC \(nih.gov\)](#)). The Yoga sessions will be virtual and study participants will be able to complete these sessions at home. The session will not be recorded. They will be free of cost for the study participants. Yoga that will be taught is a simple form of exercise that is tailored to people with a history of TBI. The movements are slow and study participants will have the choice to participate up to their comfort level. The role of LoveYourBrain will be to administer the yoga intervention and will not be engaged in the research study.

To be included, they should:

1. Have low PTG (PGI-X score <75)
2. Be inexperienced/novice yoga users
3. Not be receiving rehab services (per [name] on 6/12/2023: exclude anyone who is receiving counseling, psychiatry, PM&R, neuro, OT, psychotherapy, social work etc.)

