#### INCENTIVES

Participants will receive \$40 and the 30 who participate in the Yoga intervention will receive another \$60 for completing all 6 weeks of the intervention.

For the 15 Wait list controls, who participate in the Yoga intervention and complete the follow up survey will receive \$30.

The intervention group participants who have completed 3 or more LYB yoga sessions and who have completed the week-20 follow up survey will receive \$30 incentive.

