## LIMITATIONS OF THE STUDY

First and foremost, this study is limited to female concussion survivors only and as such, is not generalizable to men who experience TBI. Secondly, the study is recruiting from the PINK concussion group, so the study cannot be generalizable to anyone not in this group, and/or all females with TBI. As this is a pilot, the Yoga intervention will have only 30 participants therefore there's the potential for Type 2 error (false negatives). We will need a larger, more powered study -ideally a clinical trial-to determine the true effect of the Yoga intervention.

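### Aim 2 judges yoga by a before/after paired t-test in women selected for low PTGI-X scores, and no stated analysis compares them with the planned wait-list arm

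*Combined protocol and SAP*

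**What the plan says.** The Aim 2 hypothesis in the Background is within-group: scores are expected to go up after yoga in women with low PTG. The Data Analysis Plan follows it: "For Aim 2, we will use paired t-test to compare the mean difference in PTG scores and domains before and after the yoga intervention". The rest of that sentence presents this as the test of whether yoga works.

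The section on the LYB Yoga intervention makes a low value of the outcome an entry condition: "Have low PTG (PGI-X score <75" (on the 0 to 125 scale). It also states: "Thirty participants will be randomly selected to participate in the LYB Yoga intervention".

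The Data Analysis Plan then describes two groups: "We will administer the PTG surveys again at 7 weeks and 30 days to 15 Yoga and 15 Wait list controls". It adds: "The 15 Wait list controls will do the LYB program after the 30-day PTG surveys have been completed". A control period is therefore planned, but no sentence compares the two groups. The chi-square and logistic models compare low with high PTG, and the remaining Aim 2 items are feasibility and acceptability measures.

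The Limitations section says of the sample of 30: "therefore there's the potential for Type 2 error (false negatives". It calls for a larger study, preferably a clinical trial, and does not mention regression to the mean or uncontrolled change.

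**The concern.** A woman's PTGI-X score on a given day is part stable level and part day-to-day variation. Selecting scores below 75 picks out women whose variation happened to be downward, and on retest that part returns towards zero. If the qualifying score is the before value, the paired test credits this rise to yoga. It also cannot separate yoga from the passage of time or repeat testing.

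The Aim 2 hypothesis could then be declared supported far more often than the nominal rate when yoga has no effect. The domain tests under Aim 2b share the problem to the extent that domain scores drive the qualifying total. The upward bias would also carry into the planning of the larger trial. The Limitations warn of false negatives only, while the stated test inflates false positives.

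**Working it through.** **The plan's own figure.** No sample size or power is given for Aim 2. The survey size of 350 reproduces as 1.96² × 0.35 × 0.65 / 0.05² = 349.6 if an unstated margin of 5 points is assumed, but it does not bear on Aim 2.

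**Inputs from the document.** The cut-off is 75 on a 0 to 125 scale. There are 15 women per group. Alpha is 0.05, taken as two-sided because the plan does not say. Prevalence of low PTG is 35%, varied upward to 50% and 65% because the Aim 1a hypothesis reads "at least 35% of the study sample will have low PTG".

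**Assumptions not in the document.** Normal scores, no yoga effect, SD 20 to 25, test-retest correlation r of 0.6 to 0.9, and the qualifying score used as the before value.

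**Step 1: expected rise with no effect.** For a normal score selected to lie in the lowest fraction p,

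rise = (1 − r) × SD × φ(z_p)/p

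where φ(z_p)/p is 1.058 at p = 0.35, 0.798 at 0.50 and 0.570 at 0.65.

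| Prevalence of low PTG | r = 0.6, SD 25 | r = 0.9, SD 20 |
|---|---|---|
| 35% | 0.4 × 25 × 1.058 = 10.6 points | 0.1 × 20 × 1.058 = 2.1 points |
| 50% | 8.0 points | 1.6 points |
| 65% | 5.7 points | 1.1 points |

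**Step 2: how often the paired test misleads.** In SD units, the variance of a selected baseline is v = 1 − z_p·λ − λ², with λ = φ(z_p)/p. At p = 0.35, z_p = −0.385, so v = 1 + 0.408 − 1.120 = 0.288. The SD of the change is √[(1 − r)²v + 1 − r²].

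- At r = 0.6 the mean change is 0.4 × 1.058 = 0.423 and its SD is √(0.16 × 0.288 + 0.64) = 0.828. The noncentrality is 0.423/0.828 × √15 = 1.98. With 14 degrees of freedom and a critical value of 2.145, the chance of a significant rise is 0.454.
- At r = 0.9 the mean is 0.106 and the SD 0.439. The noncentrality is 0.93 and the chance about 0.138.

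This probability does not depend on the SD of the score. Simulation with 40,000 trials per cell agrees. The share of trials significant for improvement (nominal 2.5%) in 15 yoga women is:

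| Prevalence | r = 0.6 | 0.7 | 0.8 | 0.9 |
|---|---|---|---|---|
| 35% | 45% | 34% | 24% | 14% |
| 50% | 28% | 21% | 15% | 10% |
| 65% | 16% | 13% | 10% | 7% |

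Rounding scores and clipping them to 0 to 125 leaves the 35% and 50% rows essentially unchanged.

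**Step 3: other readings of the before value.** If all 30 are pooled, with the wait-list women measured from their later pre-yoga survey, the rate is 23% to 9% at 35% prevalence. If all 30 were measured from screening it would be 77% to 25%, but that ignores the wait-list women's later surveys. Measured from the later survey, wait-list women alone give 2.4% to 2.6%, which is nominal.

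**Step 4: the comparison not stated.** ANCOVA of follow-up PTGI-X on arm and baseline, 15 versus 15 and randomly assigned, rejects in about 5% of null trials two-sided, or about 2.5% in the direction of improvement, in every scenario. At SD 25 the 95% CI half-width is 15.1, 13.5, 11.4 and 8.2 points for r = 0.6, 0.7, 0.8 and 0.9.

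**The case against.** The strongest objection is that the before value is inferred. The plan does not say that the yoga arm's baseline is the qualifying score. The inference rests on the surveys being given again and on no pre-yoga survey being described. Figure 5, cited for the schedule, is not shown and might contain a fresh baseline or an arm comparison. Step 3 shows that a fresh baseline would remove most of the inflation. This stands as a condition on the size of the inflation. It does not rescue the test, which would still be uncontrolled, and the written analysis would still need to say so.

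The SD and r are also assumptions, and the low end, 7% against 2.5%, is modest. That is correct. The direction of the bias follows from the selection, and every cell exceeds twice nominal.

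The plan does point towards random allocation: the sentence on selecting the 30 links to an overview of randomisation techniques, and the second group is called controls. The split itself is still not described.

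ANCOVA is not the only valid choice. A between-arm t-test on change scores also holds its error rate (4.9% to 5.1%). ANCOVA is preferred for precision.

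Finally, this is a pilot and the plan defers the true effect to a larger study. That softens the harm, but the paired test is still offered as the evidence that yoga works.

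**Conclusion.** The concern holds. As written, Aim 2 would be decided by an uncontrolled before/after test in women selected on the outcome, while the control data it needs are collected and given no stated use. If the qualifying score is the before value, the false-improvement rate in 15 women is about 45% to 14% at the plan's 35% prevalence and about 16% to 7% at 65%, against 2.5%. These ranges assume normal scores, no yoga effect and r of 0.6 to 0.9. The absence of a stated arm comparison depends on none of these assumptions, only on the readable text. This should be corrected before the Aim 2 data are analysed.

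**What to change.** 1. State whether the 30 women are randomised 15:15 to yoga or wait list. If not, label the comparison non-randomised.
2. State which survey is each arm's baseline, and the origin of the 7-week and 30-day surveys. Reconcile them with the programme length implied by the Incentives section ("for completing all 6 weeks of the intervention") and with the wait-list start. If both are counted from baseline and yoga starts then, day 30 falls inside the 42-day programme, and the wait-list arm could have up to 49 − 30 = 19 days of yoga before the 7-week survey. If the 30 days run from the end of the programme or from the 7-week survey, the conflict disappears.
3. Make the Aim 2 analysis yoga versus wait list at a common survey confirmed to precede the wait-list arm's start: ANCOVA of PTGI-X total on arm and baseline PTGI-X, by assigned group, reported as a difference with 95% CI.
4. Use the same model for the PTGI-X domains, as exploratory estimates with intervals and no significance claims.
5. Keep the paired t-tests as descriptive only, and add regression to the mean to the Limitations.

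The cost is wording only, using surveys already planned, provided the split is random and a common survey precedes the wait-list start. If the split is not random, the label in item 1 applies. If no such survey can be confirmed, the timing must be reconciled first. The price is precision: a 95% CI of about ±13.5 points at an assumed SD of 25 and r of 0.7, and roughly 80% power only for differences of about 12 to 21 points at that SD (r of 0.9 to 0.6). A pilot can accept a wide interval more readily than a biased estimate.
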